A community-based music enrichment program to address health and developmental disparities during early childhood

NCT05868811

7-3-2025

Study Protocol

The study procedures were approved by the Institutional Review Board at Children's Mercy Hospital. Interested parents were screened via an online questionnaire or in-person interview at a hospital-affiliated primary care clinic. Eligible families were scheduled for two baseline assessment visits: a home visit (~45 min) followed by a lab visit (~45 min). When researchers arrived at the home, parents were given a brief description of study protocols and completed a consent form for their participation and the infant's participation. During the visit, parents filled out study questionnaires. Parents were then provided with instructions to record two days of the infant's natural language environment using the Language Environment Analysis (LENA) devices. Before leaving their home, parents scheduled their second lab assessment visit. This visit was scheduled during a time when the parent felt the infant would be awake, alert, and willing to do the food/non-food reinforcement task. Parents were instructed to avoid feeding their child one hour prior to the visit and to provide the infant's favorite solid food for the food portion of the task. Upon the family's arrival to the lab, researchers interacted with the infants, establishing rapport by using toys and reading books. While infants became familiar with the researchers, parents completed study questionnaires. This orientation period lasted 5–10 min, until the infant had acclimated to their surroundings, as confirmed by the parent. Then, the child was placed in a highchair next to the parent to avoid separation anxiety and stranger anxiety. Parents were informed not to interact with the child during any of the research tasks. After the food/non-food reinforcement task, research staff measured the height and weight of the parent and infant.

After completing both baseline assessment appointments, families were randomly assigned to the music or control group. Families completed follow-up assessments using the same procedure after their first semester (8-week) and second semester (16-week). When possible, the same research staff ran appointments so that families remained familiar with the staff, especially the researcher who delivered the reinforcers to the infants. Lastly, we sent out a parent satisfaction survey via email to all enrolled families to assess the acceptability of the intervention.

Data Analysis Plan

Group baseline characteristics were compared using ANOVA or Pearson's chi-square test for frequency data. We performed an intention-to-treat analysis using all randomly assigned participants, including participants who dropped out of the program. The primary outcomes (RRV_{food} and home environmental enrichment measures) were analyzed with a mixed-model ANOVA, which handles missing data at random using maximum likelihood estimation and retains all randomly assigned subjects in the analysis. In an effort to choose a reasonably fitted model satisfying the model assumptions, the residual plots and the residual-based fit statistics, such as Akaike's Information Criterion, for various covariance structures were examined. The models included group, time (base- line, mid-, and post-intervention), and the group

× time interaction as class variables using the unstructured (UN) covariance structure. As a sensitivity analysis, we also performed repeated measures ANOVA for those who had complete data for all timepoints (i.e., the completers). Effect sizes were reported as partial eta squared for mixed model ANOVA, and eta-squares were converted to Cohen's f to ease model comparison. Effect sizes for repeated measures ANOVA similarly were computed from partial eta square and converted to Cohen's f using G*Power 3.1.9.6. Though p -values can inform whether an effect exists, Cohen's f can help to assess the strength of that effect and contextualize the results. Given the small sample size, we focus on interpreting group differences when there are medium (0.25) to large (0.4) effect size estimates. Since our study is a pilot study, knowing the expected effect size can inform power analyses for sample size determination of a future larger RCT. All models were performed using PROC MIXED in SAS version 9.4 (©2020, SAS Institute, Cary, NC, USA).

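### Maximum likelihood with an unstructured covariance in a small sample, with no REML or denominator-df method stated, makes the group × time p-values anti-conservative

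*Combined protocol and SAP*

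**What the plan says.** All of this is in the Data Analysis Plan.

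- **Estimator.** The primary outcomes (RRV food and the home enrichment measures) are analysed with a mixed-model ANOVA, "which handles missing data at random using maximum likelihood estimation and retains all randomly assigned subjects in the analysis".
- **Model.** "The models included group, time (base- line, mid-, and post-intervention), and the group" × "time interaction as class variables using the unstructured (UN) covariance structure". Three visits under an unstructured covariance means six covariance parameters, and the interaction in a two-arm trial has 2 numerator df.
- **Population.** Intention to treat, "using all randomly assigned participants, including participants who dropped out of the program".
- **Sample size.** No number is given. The text says "Given the small sample size, we focus on interpreting group differences" when the effect size is medium or large.
- **Software.** "All models were performed using PROC MIXED in SAS version 9.4". No estimation or denominator-df option is named.
- **Role of p-values.** The plan says that p-"values can inform whether an effect exists", while Cohen's f conveys the strength of the effect.

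REML, Kenward-Roger, Satterthwaite and small-sample standard errors are not mentioned anywhere. Nor does the plan say that none of them was used.

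**The concern.** Two separate small-sample problems arise if the model is run as described.

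1. Maximum likelihood divides by N rather than by the residual df. With two arms and complete data, the estimated variances are too small by the factor (N-2)/N.
2. The Wald F statistic treats the estimated covariance matrix as known. Six parameters estimated from a few dozen families are not known, and a reference distribution with N-2 denominator df does not allow for that.

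Both errors make p-values too small, and dropout adds to them because later visits contribute less information on the covariance. The group × time interaction is the test of the intervention for each primary outcome. At stake are its p-value and the standard errors of the group differences in change.

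**Working it through.** **Inputs from the plan:** two arms, three visits, unstructured covariance, maximum likelihood, a 2-df interaction test.

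**Assumptions, because the documents give no values:** total N of 20 to 100, equal arms, nominal 5% test, denominator df N-2. The dropout runs also assume normal data, a correlation of 0.5 between visits, and random loss of 15% after baseline and a further 10% after the mid visit. The plan states no figure to reproduce.

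**Step 1: complete data (exact).** Under the null, Hotelling's T² for the 2-df interaction satisfies

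T²(N-3)/[2(N-2)] ~ F(2, N-3).

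The REML Wald F is T²/2. The ML Wald F is larger by N/(N-2). Referring each to the 5% critical value Fcrit of F(2, N-2) gives

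- ML size = P[F(2, N-3) > Fcrit × (N-3)/N]
- REML size = P[F(2, N-3) > Fcrit × (N-3)/(N-2)]

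Example, N = 30: Fcrit(2, 28) = 3.340.

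- ML: 3.340 × 27/30 = 3.006, and P[F(2, 27) > 3.006] = 6.6%.
- REML: 3.340 × 27/28 = 3.221, and P[F(2, 27) > 3.221] = 5.6%.

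| N | Fcrit(2, N-2) | ML size | REML size | ML SE / REML SE = √((N-2)/N) |
|---|---|---|---|---|
| 20 | 3.555 | 7.5% | 5.9% | 0.949 |
| 30 | 3.340 | 6.6% | 5.6% | 0.966 |
| 40 | 3.245 | 6.2% | 5.4% | 0.975 |
| 60 | 3.156 | 5.8% | 5.3% | 0.983 |
| 100 | 3.089 | 5.5% | 5.2% | 0.990 |

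**Step 2: 25% lost by 16 weeks (simulation under the null).** ML columns: 20,000 runs per N, simulation error about 0.2 points on the size. REML and Kenward-Roger columns: about 3,500 to 3,900 runs, error about 0.4 points.

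| N | ML, df N-2 | ML SE of 16-week difference in change, below true value by | REML, df N-2 | REML with Kenward-Roger |
|---|---|---|---|---|
| 20 | 9.8% | 9% | 7.9% | 5.4% |
| 30 | 7.6% | 5% | 6.3% | 5.1% |
| 40 | 7.1% | 4% | 5.6% | 4.8% |
| 60 | 6.3% | 3% | 6.0% | 5.3% |
| 100 | 5.7% | 2% | not run | not run |

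As a check on the Kenward-Roger calculation, at N = 30 with complete data it returns 27 df, which is N-3, and a size of 5.3% (2,535 runs).

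**Step 3: sensitivity to the dropout rate and df.** A separate simulation (10,000 runs at N = 20 and 30, 5,000 at N = 40 to 90) used 20% and 35% dropout.

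- ML with df N-2: 8.9% and 12.1% at N = 20; 7.7% and 8.6% at N = 30; 7.0% and 7.4% at N = 40; 5.6% and 6.2% at N = 90.
- Larger df choices make it worse. With the number of observations minus 6, ML reaches 11.0% and 14.2% at N = 20. Of the three df choices tried, N-2 is the smallest, so it gives the least inflation.
- REML with Kenward-Roger stayed between 4.7% and 5.7% in every scenario, N = 20 to 90 and dropout 0 to 35%.

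**Step 4: effect on Cohen's f.** Taking f = √(2F/(N-2)), ML inflates f over REML by √(N/(N-2)) with complete data: 5.4%, 3.5%, 2.6% and 1.7% at N = 20, 30, 40 and 60. With 25% lost, the median inflation is 6.6%, 4.3%, 3.2% and 2.1%.

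**The case against.** The strongest reply is that the documents do not establish what was run. The maximum likelihood wording describes how the mixed model treats missing data, in contrast to the completers analysis, and may be loose language for any likelihood-based fit. No df method is stated, so N-2 is an assumption. N, dropout and alpha are also unknown, and with REML and complete data the excess is below one percentage point at every N considered. Moreover, this is a pilot with no stated significance rule, interpretation is led by effect size, and f barely moves. The completers' repeated-measures ANOVA gives a partial cross-check, since the classical form of that test does not use the ML divisor. Finally, Kenward-Roger is only one of several acceptable corrections.

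Much of this stands. The size cannot be fixed from the documents, the reading of f at 0.25 and 0.4 is essentially unaffected, and another stated small-sample df and standard-error method could also serve.

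It does not remove the point. Under the literal text the test is anti-conservative at every N, dropout rate and df choice tried. Under REML the missing df method still matters when families drop out: about 7.9% at N = 20 and 6.3% at N = 30. The 5.6% at N = 40 is within simulation error of 5%, but the separate simulation found 6.1% to 6.3% there. The completers analysis discards the dropouts and does not correct the primary model. And the plan does use p-values as evidence that an effect exists.

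**Conclusion.** The concern holds. Taken as written with N-2 df, the stated method gives standard errors and group × time p-values that are too small. For a nominal 5% test the true type I error is about 6% to 10% at N of 20 to 40, depending on N and on whether 0 or 25% are lost, and about 5.5% to 5.7% at N = 100. If REML was used instead, the first problem disappears and the second remains, with a smaller excess.

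These figures rest on assumed N, alpha, correlation, normal data and completely random dropout. Dropout that depends on earlier observed values was not simulated. The direction is secure under the literal reading, but the size in this trial is not known. The point concerns p-values and standard errors and does not undermine the effect-size interpretation. It should be corrected, but it is not fatal to the pilot.

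**What to change.** First, state which estimator and denominator-df method were used, along with N and dropout by arm.

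Then specify REML with Kenward-Roger for the primary models, keeping the unstructured covariance: `METHOD=REML` on the PROC MIXED statement and `DDFM=KR` on the MODEL statement. With complete data this reproduces the exact F test on (2, N-3) df. If maximum likelihood or default df was used, refit and report the p-values and standard errors from that fit. If an adequate small-sample method was already used, one added sentence is enough.

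The cost is two options in software already in use. Because the plan is written in the past tense, a refit may also mean re-reporting results. P-values and standard errors would rise slightly, and Cohen's f would hardly change.

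### Baseline is measured before randomisation but has its own mean in each arm, so the group × time test compares changes from baseline: valid, but usually less precise than a common-baseline-mean model with a small-sample correction

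*Combined protocol and SAP*

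**What the plan says.** The Study Protocol puts assignment after baseline: "After completing both baseline assessment appointments, families were randomly assigned to the music or control group". Follow-up is at 8 and 16 weeks.

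The Data Analysis Plan gives the primary model: "The models included group, time (base- line, mid-, and post-intervention), and the group" × time interaction, all as class effects, with unstructured (UN) covariance in PROC MIXED. It says the method "handles missing data at random using maximum likelihood estimation" and "retains all randomly assigned subjects in the analysis", "including participants who dropped out of the program". For sensitivity, "we also performed repeated measures ANOVA for those who had complete data for all timepoints".

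On reporting, "Effect sizes were reported as partial eta squared for mixed model ANOVA", then converted to Cohen's f. Interpretation rests on f: "Given the small sample size, we focus on interpreting group differences when there are medium (0.25) to large (0.4) effect size estimates". The plan wants these effect sizes to feed the power calculation of a larger RCT.

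It names no baseline covariate, common-baseline constraint, REML or denominator-df method. It gives no sample size, SD, correlation, dropout rate or significance level.

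**The concern.** Two arms by three visits gives six free means, two of them at baseline. Randomisation after baseline makes those two equal in truth, so any observed baseline difference is chance. The planned interaction subtracts that chance difference in full. A model with one baseline mean removes only the part that predicts follow-up.

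Two things are at stake. The first is precision: intervals may be wider than the data allow in a study that stresses how small it is. The second is the meaning of Cohen's f. The same true effect gives a different f under each model, so an f passed to a later RCT without its model can lead to the wrong sample size.

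**Working it through.** **Inputs.** From the documents: baseline before randomisation, three visits, group × time with UN covariance, f thresholds of 0.25 and 0.4. The documents state no figure to reproduce. Assumed: 1:1 allocation, N = 40 or 20 families, correlation ρ = 0.3/0.5/0.7 between any two visits, follow-up SD k times baseline SD (k = 1 or 1.25), true effects of 0.3 and 0.6 baseline SD at 8 and 16 weeks, 5% level. Triplets below follow that order of ρ.

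**1. Variance of a follow-up contrast, complete data.** Let n = N/2 per arm, with SDs s0 at baseline and s1 at follow-up.

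- Planned: (2/n)(s0² + s1² − 2ρ·s0·s1).
- Common baseline mean: (2/n)·s1²(1 − ρ²) × [1 + 1/(N − 4)]. The bracket is the cost of estimating the slope.
- Before the slope cost, planned minus common is (2/n)(s0 − ρ·s1)², which is never negative and is zero when ρk = 1.

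Equal SDs: the ratio common/planned is [(1 + ρ)/2] × [1 + 1/(N − 4)].

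- N = 40, slope cost 1 + 1/36 = 1.028: 0.65, 0.75 and 0.85 times 1.028 = 0.668/0.771/0.874.
- Break-even ρ: 2/1.028 − 1 = 0.946 at N = 40. At N = 20 the slope cost is 1 + 1/16 = 1.0625 and break-even is 2/1.0625 − 1 = 0.882.

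k = 1.25, ρ = 0.7: planned 1 + 1.5625 − 1.75 = 0.8125; common 1.5625 × 0.51 = 0.797; ratio 0.981. Times 1.028 this is 1.008 at N = 40; times 1.0625 it is 1.042 at N = 20.

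**2. Simulation of both models** (REML, Kenward-Roger; dropout completely at random, half after baseline and half after 8 weeks). The ratio is the variance of the 16-week contrast, common/planned. Power is for the 2-df test.

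| N | k | Dropout | Variance ratio | Power, planned (%) | Power, common (%) |
|---|---|---|---|---|---|
| 40 | 1 | 0 | 0.66/0.77/0.87 | 26/35/55 | 40/46/62 |
| 40 | 1 | 20% | 0.73/0.82/0.91 | 22/30/47 | 33/38/52 |
| 40 | 1 | 40% | 0.79/0.87/0.94 | 19/24/38 | 26/30/41 |
| 40 | 1.25 | 0 | 0.80/0.91/1.01 | 21/28/43 | 27/31/42 |
| 40 | 1.25 | 40% | 0.90/0.97/1.03 | 15/19/28 | 18/20/28 |
| 20 | 1 | 0 | 0.68/0.78/0.89 | 13/18/27 | 19/22/30 |
| 20 | 1.25 | 0 | 0.82/0.94/1.04 | 11/14/20 | 14/15/20 |

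In the first row the 16-week 95% CI half-width falls from 0.75/0.64/0.49 to 0.62/0.56/0.46 SD.

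**3. Effect on f and RCT size.** Population f = √(d′S⁻¹d/4), with d = (0.3, 0.6) and S the covariance of the changes (planned) or of the baseline-adjusted follow-ups (common).

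- k = 1: f = 0.254/0.300/0.387 planned, 0.326/0.352/0.422 common. Families for 80% power on 2 df: about 154/112/68 against 94/82/58 (96/82/60 if the slope cost is charged).
- k = 1.25: f = 0.224/0.263/0.334 against 0.261/0.281/0.338; families 196/144/90 against 146/126/88.

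**4. Type I error of the 2-df test, nominal 5%.**

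| N | Dropout | Planned, N−2 df | Planned, KR | Common, N−2 df | Common, KR |
|---|---|---|---|---|---|
| 40 | 0 | 5.4% | 4.9% | 6.2% | 4.9% |
| 40 | 40% | 6.3% | 4.9% | 7.8% | 5.2% |
| 20 | 0 | 5.8% | 4.9% | 7.8% | 5.1% |
| 20 | 40% | 8.5% | 5.3% | 12.1% | 5.8% |

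The uncorrected columns use REML. If the plan's wording means ML variances with N − 2 df, the exact error of the planned test with complete data is 6.2% (N = 40) and 7.5% (N = 20).

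**The case against.** The strongest reply is that nothing in the plan is wrong. Group × time under UN is a legitimate choice, and the benefit of changing it rests on assumed values. Nothing in the documents shows that ρ and k for RRV_food or the home enrichment measures fall where the gain is real. This stands: the algebra is certain, the gain for a given outcome is not.

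The planning argument is also open to challenge. The f values above are population values, and a pilot estimate is noisy and biased upward. At N = 40, ρ = 0.3, k = 1 and complete data, the median estimated f is 0.32 (10th to 90th percentile 0.14 to 0.53) planned and 0.39 (0.19 to 0.61) constrained. With no effect at all, f still reaches 0.25 in 33% and 34% of trials, and at N = 20 in 60% and 62%. So the change does not cure the weakness of reading results by f thresholds. An f from the planned model is also coherent for an RCT analysed the same way, and reporting SDs and correlations alone would let planners convert. These points stand as limits. They support labelling f and reporting its ingredients; they do not defend an unlabelled f.

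Third, the small-sample correction protects type I error rather than precision, and it would help the planned model too. True, but the constrained model needs it more, so the two belong together.

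Finally, the change can cost something. With k = 1.25, ρ = 0.7 and dropout at N = 40, variance is about 3% worse. At N = 20 with 40% dropout it is about 6% worse. These losses are small beside the gains at lower correlation.

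**Conclusion.** The point holds, as a cheap improvement and not as an error. The planned contrast is valid and unbiased. It ignores a baseline equality that randomisation guarantees, and with similar SDs over time it is less precise except at very high correlation. At N = 40 with equal SDs, the common-baseline model cuts the 16-week variance by about 13% to 34% without dropout and 6% to 21% with 40% dropout, for correlations of 0.7 down to 0.3. With follow-up SD 1.25 times baseline, the gain shrinks and is nil or slightly negative at correlation 0.7. All of this rests on assumed N, correlations, SDs, effects and dropout completely at random. The benefit therefore cannot be claimed for every primary outcome.

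**What to change.** Keep PROC MIXED, UN covariance and every randomised family. Then:

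- Constrain the arms to one baseline mean: time plus group × post-baseline time, with no group term at baseline.
- State REML and a small-sample correction to standard errors and denominator df (for example ddfm=kr). Do not use the constrained model without it.
- Test the 8- and 16-week group effects jointly on 2 df.
- For each outcome report both adjusted music-minus-control differences with 95% CIs, the SD at each visit and the baseline-to-follow-up correlations, so that outcomes with no gain are visible.
- Take f from the corrected test, f = √(2F / denominator df), and label it with its model.
- In the completers' analysis, model the 8- and 16-week values with baseline and baseline × time as covariates, and take f from the same 2-df group test. No completer is lost and the two analyses stay comparable.

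The cost is model code and SAP wording, with no new data. Estimating the slope adds about 3% to the variance at N = 40 and 6% at N = 20, already counted above. Some excess type I error remains at N = 20 with 40% dropout: 5.8%, against 5.3% for the planned model with the same correction. The plan is written in the past tense, so if results exist this should be reported as a disclosed supplementary analysis beside the planned one, not as a replacement.

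### The group comparison is summed up by Cohen's f, which has no sign and, if taken from the group-by-time term, no time point; a signed, baseline-adjusted 16-week difference should be reported beside it

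*Combined protocol and SAP*

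**What the plan says.** All the relevant text is in the combined protocol and SAP, under Data Analysis Plan.

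- **Design.** After baseline, "families were randomly assigned to the music or control group". Follow-up assessments are at 8 and 16 weeks.
- **Model.** "The models included group, time (base- line, mid-, and post-intervention), and the group" by "time interaction as class variables using the unstructured (UN) covariance structure". With two groups and three time levels, the interaction has (2 − 1)(3 − 1) = 2 degrees of freedom.
- **Effect size.** "Effect sizes were reported as partial eta squared for mixed model ANOVA", and "eta-squares were converted to Cohen's f to ease model comparison".
- **Interpretation.** "Given the small sample size, we focus on interpreting group differences when there are medium (0.25) to large (0.4) effect size estimates".
- **Later use.** The plan calls the study a pilot and says that the effect size can inform the power analysis of a larger trial.

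The plan does not say which term, the group main effect or group by time, is the group comparison. It names no contrast, no primary time point, no expected direction and no confidence interval for a group difference. It gives no sample size, alpha, SD or visit correlation.

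**The concern.** Cohen's f is a ratio of variation between means to error variation. It is never negative, so music families doing better and music families doing equally worse give the same value. On a 2-df interaction it also pools the 8-week and 16-week changes into one number, so it does not say when the groups differed.

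That matters because f has two jobs in this plan. It decides which group differences are interpreted, and it is the quantity carried forward to a larger trial. A later trial that compares groups at the end of the program needs the size and direction of the 16-week difference and its SD, and f does not supply them.

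**Working it through.** The plan states no N, power or alpha, so there is no figure of its own to reproduce.

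**Inputs.** From the plan: two groups, and visits at baseline, 8 and 16 weeks. Assumed: 1:1 allocation, equal SDs (so effects are in SD units), correlation r equal between all visits (0.3, 0.5 or 0.7), complete data, alpha 0.05, and total N of 40 or 60. Positive values favour music.

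**1. f for different effect patterns.** Let a and b be the group differences in change from baseline at 8 and 16 weeks. The noncentrality is λ = e′V⁻¹e, with e = (a, b) and V = (4/N)(1 − r)[[2, 1], [1, 2]]. Taking f² = λ/N gives

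f² = (a² − ab + b²) / [6(1 − r)].

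At r = 0.5 the denominator is 3. For (0, 0.6), f² = 0.36/3 = 0.12, so f = 0.346. For (0.3, 0.6), f² = (0.09 − 0.18 + 0.36)/3 = 0.09, so f = 0.300.

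| Pattern (8, 16 weeks), SD | r = 0.3 | r = 0.5 | r = 0.7 |
|---|---|---|---|
| Late (0, 0.6) | 0.293 | 0.346 | 0.447 |
| Sustained (0.6, 0.6) | 0.293 | 0.346 | 0.447 |
| 8-week only (0.6, 0) | 0.293 | 0.346 | 0.447 |
| Sustained harm (−0.6, −0.6) | 0.293 | 0.346 | 0.447 |
| Building (0.3, 0.6) | 0.254 | 0.300 | 0.387 |

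An f of 0.35 at r = 0.5 thus fits a true 16-week effect of 0.6, 0 or −0.6 SD. An effect that has vanished by 16 weeks scores higher than one that grows over both semesters.

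**2. What depends on the assumptions.** Replacing (a, b) by (−a, −b) leaves λ unchanged under any covariance, so the blindness to sign is general. Exact equality of the 8-week-only and sustained patterns needs equal correlations. Under an AR(1) pattern with adjacent correlation 0.5, an 8-week-only effect of 0.41 SD gives the same λ as a sustained effect of 0.5 SD. The level of f also depends on the error df used to form it: at N = 40, dividing λ = 4.8 by 2(N − 2) = 76 in place of N gives √0.063 = 0.25. The ties in the table are unaffected.

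**3. Power at r = 0.5.** For a 16-week effect d:

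- 2-df interaction: λ = Nf², referred to F(2, N − 3).
- Unadjusted 16-week change: λ = Nd²/[8(1 − r)], referred to F(1, N − 2). At N = 40 and d = 0.6, 14.4/4 = 3.6.
- Baseline-adjusted 16-week difference: λ = Nd²/[4(1 − r²)], referred to F(1, N − 3). At N = 40 and d = 0.6, 14.4/3 = 4.8.

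| Pattern | N | 2-df | 16-week change | 16-week adjusted |
|---|---|---|---|---|
| Building (0.3, 0.6) | 40 | 35% | 46% | 57% |
| Building (0.3, 0.6) | 60 | 51% | 63% | 75% |
| Late or sustained | 40 | 45% | 46% | 57% |
| Late or sustained | 60 | 64% | 63% | 75% |
| Fading (0.6, 0.3) | 40 | 35% | 15% | 19% |
| 8-week only (0.6, 0) | 40 | 45% | 5% | 5% |

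Baseline adjustment raises the power of the 16-week contrast in every pattern that has a 16-week effect.

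**The case against.** Four points stand, at least in part.

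- **The premise is inferred.** The plan never says that group by time decides the comparison. The group main effect would be no better summary: its f is also unsigned, and it averages in the pre-randomisation baseline.
- **Direction is not lost.** The sentence "we focus on interpreting group differences when there are medium (0.25) to large (0.4) effect size estimates" says where to look, and what is then interpreted is a group difference. Fitted means would show its direction, and nothing says they will be withheld. A reader might infer that benefit and harm would be confused in the report; the documents do not support that. What is missing is a planned signed estimate with its uncertainty.
- **The omnibus test is not generally weaker.** A reader might infer that a 16-week contrast should replace it. That gains only if the effect builds, a pattern the documents never predict. For late or sustained effects the unadjusted contrast ties at N = 40 and is slightly behind at N = 60. Under AR(1) correlation of 0.7 it has 45% against 56% at N = 40. With both tests baseline-adjusted, the 2-df test leads for a sustained effect, 63% to 57% at N = 40. For 8-week-only or fading effects the omnibus test is much better. Choosing between them is a trade-off.
- **Timing.** The plan is written in the past tense, so a contrast added now may be post hoc.

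None of this supplies what f lacks for the next trial. An interaction f could size a repeat of the same omnibus test under the same correlations, but not a comparison of groups at 16 weeks.

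**Conclusion.** The point holds as one about reporting and estimation. The plan's only named effect size is unsigned and, if it comes from the 2-df interaction, tied to no time point. It nevertheless selects what is interpreted and is offered for a later trial's sample size. At an assumed correlation of 0.5, four different patterns of 0.6 SD share f = 0.35; the shared value is 0.29 at correlation 0.3 and 0.45 at 0.7.

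The blindness to sign rests on no assumption. The tie between 8-week-only and sustained effects needs equal correlations. The power figures rest on the assumed N, alpha, correlation, effect size and complete data.

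The material does not support a general loss of power from the 2-df test, or demoting it. The supported power gain comes from using the baseline already collected: 46% to 57% at N = 40 and 63% to 75% at N = 60 for a 0.6 SD effect at 16 weeks. In a pilot, the estimate handed to the next trial matters more than power.

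**What to change.** Keep the 2-df interaction and f. For each primary outcome, add the signed music-minus-control difference at 16 weeks, and also at 8 weeks, adjusted for baseline, with a 95% CI and a standardised difference. State which direction favours the program. Base the future trial's sample size on the 16-week estimate, its CI and its SD, and not on f alone. The interval will be wide: at N = 40 and correlation 0.5 the adjusted standard error is √(4 × 0.75/40) = 0.27 SD, or about ±0.55 SD.

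This needs a small re-specification in PROC MIXED: either baseline as a covariate with the two follow-ups as responses, or baseline kept as a response with its mean constrained equal across groups. An ESTIMATE statement in the current model gives only the unadjusted difference in change.

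The cost is that second model specification and a few more reported estimates. No new data are needed. If the data have already been analysed, label the added estimates post hoc.

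### The completers' analysis is named as a different model from the primary one, so a difference in Cohen's f between the two cannot be attributed to the families left out

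*Combined protocol and SAP*

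**What the plan says.** All of this is in the Data Analysis Plan section of the combined protocol and SAP.

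- **Primary analysis.** The primary outcomes were "analyzed with a mixed-model ANOVA, which handles missing data at random using maximum likelihood estimation and retains all randomly assigned subjects in the analysis". The models contain group, time at three visits, and the group by time "interaction as class variables using the unstructured (UN) covariance structure".
- **Sensitivity analysis.** "As a sensitivity analysis, we also performed repeated measures ANOVA for those who had complete data for all timepoints".
- **Effect sizes.** For the primary model: "Effect sizes were reported as partial eta squared for mixed model ANOVA, and eta-squares were converted to Cohen's f to ease model comparison". For the completers: "Effect sizes for repeated measures ANOVA similarly were computed from partial eta square and converted to Cohen's f using G*Power 3.1.9.6".
- **Use of f.** Interpretation concentrates on estimates between 0.25 (medium) and 0.4 (large). The effect size is also meant to inform the power calculation of a later, larger trial.
- **Software.** The closing sentence says that every model was run in PROC MIXED.

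The section gives no denominator df method for either analysis. For the completers it states no covariance structure, no sphericity assumption or correction, and no choice between the univariate and the multivariate test. It gives no sample size.

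**The concern.** A completers' analysis is informative when only the set of families changes. Here the plan gives it a different name from the primary model, and the usual meaning of that name is a univariate ANOVA that assumes sphericity. Model and population then move together.

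The common scale does not repair this. A UN mixed model has no sums of squares, so its partial eta squared has to be built from F and its df, and the resulting f depends on the error df used. Two f values from different error df need not agree even when no family is missing.

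This matters because the plan gives f the main interpretive role, with cut-offs at 0.25 and 0.4. A gap in f between the two analyses could be put down to dropout when it comes from the model, or a model difference could mask a dropout effect of the opposite sign. The later trial's power calculation is also exposed: required N goes roughly as 1/f², so a factor of 1.414 in f is a factor of about 2 in N.

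**Working it through.** The plan states no N, F, eta squared or f, so it has no figure to reproduce. The check asks how far the two f values differ on the same complete data.

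**Inputs from the plan.** Two groups ("families were randomly assigned to the music or control group") and three visits, so the group by time numerator df is (2-1)(3-1) = 2. UN covariance in the primary model.

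**Assumed inputs.** N = 20 to 60 complete cases in equal arms. The UN error df ν is N-2, 2(N-2), or residual 3N-6 = 3(N-2).

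**Formulas.** Partial eta squared is F·df1/(F·df1 + df2) and f = √(η²/(1-η²)), so f = √(F·df1/df2).

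- Univariate repeated measures ANOVA: f² = 2F/[2(N-2)].
- UN model: f² = 2F/ν.
- For equal F, the ratio f(UN)/f(univariate) = √[2(N-2)/ν].

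| UN error df ν | Ratio at equal F | Univariate f = 0.25 reads as | Univariate f = 0.40 reads as |
|---|---|---|---|
| N-2 | √2 = 1.414 | 0.35 | 0.57 |
| 2(N-2) | 1.00 | 0.25 | 0.40 |
| 3(N-2) | √(2/3) = 0.816 | 0.20 | 0.33 |

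Example at N = 30: a univariate f of 0.25 means F = 0.0625 × 56/2 = 1.75. The same F gives √(3.5/28) = 0.35 with 28 df and √(3.5/84) = 0.20 with 84 df.

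**F is not equal in practice**, so both tests were computed on the same simulated complete data sets (2,000 or more per setting, UN by REML).

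- Compound symmetry, ν = N-2: median ratio 1.42 to 1.46. At N = 20 the 10th to 90th percentiles are about 1.27 to 1.77; at N = 60, about 1.31 to 1.57.
- Non-spherical covariance (AR(1), equal or unequal variances), ν = N-2: population ratio 1.20 to 1.99 by effect pattern. Simulated medians are 1.30 to 1.84.
- ν = 2(N-2): median 1.01 to 1.03 under compound symmetry, 0.92 to 1.30 otherwise.
- ν = 3(N-2): median 0.82 to 0.84 under compound symmetry.
- UN against the multivariate test (Wilks): 1.00.
- The same UN model, df rule and estimation method in both analyses: 1.00.
- Group main effect: the same F in both (1.126 and 1.126 in a check data set), ratio 1.0.

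ML in place of REML multiplies the UN f by √(N/(N-2)): √(20/18) = 1.05 at N = 20 and √(60/58) = 1.02 at N = 60.

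**Crossing of f = 0.25 with nothing missing** (compound symmetry, correlation 0.3 or 0.7, N = 20, 40 or 60, group difference of 0 to 0.8 SD at both follow-ups):

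| UN error df ν | Only the primary reaches 0.25 | Only the completers' analysis reaches 0.25 |
|---|---|---|
| N-2 | 2% to 34% | 0% |
| 2(N-2) | 0.3% to 6% | 0.2% to 3% |
| 3(N-2) | under 1% | 2% to 23% |

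**The case against.** The strongest reply is that the models may already match. The UN structure is stated for the models in general, in the sentence before the sensitivity analysis, and the closing sentence puts every model in PROC MIXED. The completers' analysis could therefore be the same UN model on fewer families, with a ratio of 1.00. This stands as a possibility. It does not settle the matter, because the plan names two analyses, reports their effect sizes in separate sentences and speaks of comparing models. If they are the same model, the plan should say so.

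A second reply is that the plan never says the comparison of f is meant to isolate the effect of missing data, and a sensitivity analysis may legitimately vary the model. That also stands as a reading of the text. However, the primary model is justified by its handling of missing data and the sensitivity set is defined only by completeness, so the comparison invites that use.

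A reader might infer more than the documents support:

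- **That a 1.4-fold gap is built in.** It requires N-2 error df for UN and a univariate test for the completers, and neither is stated.
- **That the primary f can only be the larger.** This follows algebraically from N-2 df alone. With residual df the direction reverses.
- **That lack of a sphericity correction inflates type I error materially.** The absence is inferred from silence. For the uncorrected univariate test with epsilon 0.81 to 0.90, total type I error is about 5.1% to 6.1%, which is negligible in a pilot interpreted on effect size.

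**Conclusion.** The point holds in a limited form. On the plan's wording, model and population change together, so a difference in f cannot be assigned to the excluded families. Its possible size for group by time runs from about 0.8 to 2.0 on identical complete data, with about 1.4 the typical value under one specific pairing of df and test. It is nil for a matched UN model and, under REML, for a multivariate test or the group main effect. These figures rest on assumed N, equal arms, and assumed df and covariance patterns.

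The documents do not show that the gap exists in the analyses as run. They show that a reader cannot tell. Confidence is moderate, and the change is a cheap improvement to a secondary analysis.

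**What to change.** Run the completers' analysis as the identical PROC MIXED model: same fixed effects, UN covariance, estimation method and df method, restricted to families with all three visits. State the df method for both analyses. Report the signed 8- and 16-week group differences with confidence intervals side by side, and do not rest the comparison on the two f values. A difference between the two sets of results then comes from the families left out.

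The cost is some wording and one data restriction. Because the plan is written in the past tense, one secondary analysis may have to be rerun. The univariate ANOVA is also lost as a check on the model. If that check is wanted, report it separately, label it as a change of model, and fit it to the same completers.
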